15.4 Publication, Disclosure, and Clinical Trial Registration Policy

15.4.1 Publication and Disclosure

The investigator is obliged to provide the sponsor with complete test results and all data derived by the investigator from the study. During the study, only the sponsor may make study information available to other study investigators or to regulatory agencies, except as required by law or regulation. Except as otherwise allowable in the clinical study site

CONFIDENTIAL

agreement, any public disclosure (including publicly accessible websites) related to the protocol or study results is the sole responsibility of the sponsor.

The sponsor may publish any data and information from the study (including data and information generated by the investigator) without the consent of the investigator.

The investigator or sub-investigator needs to obtain a prior written approval from the sponsor to publish any information from the study externally such as to a professional association.

15.4.2 Clinical Trial Registration

In order to ensure that information on clinical trials reaches the public in a timely manner and to comply with applicable law, regulation and guidance, Takeda will, at a minimum register all clinical trials conducted in patients that it sponsors anywhere in the world on publicly accessible websites, JAPIC-CTI, before trial initiation.

15.4.3 Clinical Trial Results Disclosure

Takeda will post the results of this clinical trial, regardless of outcome on publicly accessible websites, JAPIC-CTI, as required by applicable laws and/or regulations.

15.5 Insurance and Compensation for Injury

Each subject in the study must be insured in accordance with the regulations applicable to the site where the subject is participating. If a local underwriter is required, then the sponsor or sponsor's designee will obtain clinical study insurance against the risk of injury to clinical study subjects.

Refer to the Clinical Study Site Agreement regarding the sponsor's policy on subject compensation and treatment for injury. If the investigator or sub-investigator has questions regarding this policy, he or she should contact the sponsor or sponsor's designee.

Appendix A Schedule of Study Procedures

Study Week ^(a)	Treatment period						W52/ Early Termination ^(b)
	W26	W29	W32	W36	W40	W46	
VISIT Number ^(c)	8	9	10	11	12	13	14
Study Day ^(d) (Day)	182	203	224	252	280	322	364
Visit Windows ^(d) (Days)	175 to 189	196 to 210	217 to 231	245 to 259	273 to 287	315 to 329	357 to 371
Informed consent	X ^(e)						
Inclusion/exclusion criteria	X						
Physical examination	X ^(f)	X	X	X	X	X	X
Skin examination	X ^(f)						X
Weight	X ^(f)				X		X
Vital signs	X ^(f)	X	X	X	X	X	X
Concomitant medications	X ^(f)	X	X	X	X	X	X
Clinical laboratory tests ^(g)	X ^(f)	X	X		X	X	X
ECG	X ^(f)				X		X
MDS-UPDRS	X ^(f)		X	X	X	X	X
QOL assessment	X ^(f)				X		X
Drug compliance	X ^(f)	X	X	X	X	X	X
Dispense investigational drug	X	X	X	X	X	X	
AE assessment ^(h)	X ^(f)	X	X	X	X	X	X

- (a) The study visit weeks in this study will be counted from the start of the treatment period in the preceding study.
- (b) For subjects withdrawn from the study after the initiation of the investigational drug in this study and before Week 52 of the treatment period, the tests, observations, and assessments scheduled for Week 52 of the treatment period should be performed within 7 days following discontinuation of treatment, whenever possible (the day of the last dose regarded as 0 day).
- (c) Visit numbers in this study will be continued from the preceding study.
- (d) Day 1 is defined as the day of first study medication administration for the treatment period in the preceding study.
- (e) Informed consent for this study must be obtained prior to tests, observations, and assessments at Week 26 of the treatment period in the preceding study.
- (f) Results of the tests, observations, and assessments at Week 26 of the treatment period in the preceding study will be used also for this study.
- (g) To be measured after fasting for at least 8 hours whenever possible. Women of childbearing potential will undergo pregnancy test as well.
- (h) AE collection in this study will begin at the initiation of the investigational drug in this study, and continued until Week 52 of the treatment period or early termination. AEs occurring between the final assessment in the preceding study and the initiation of the investigational drug in this study will be captured by the preceding study. AEs that occurred during the preceding study and persisted into this study will be followed up in this study as well.

Appendix B Responsibilities of the Investigator

1. Conduct the appropriate study in accordance with the protocol and GCP considering the rights, safety and wellbeing of human subjects.
2. When a part of the important activities related to the study are delegated to the sub-investigator or the study collaborator, prepare the lists of activities to be delegated and responsible personnel, submit the lists to the director of the site in advance to get them accepted.
3. Prepare a written informed consent form and other written information, and update as appropriate.
4. Confirm the contents of the clinical study agreement.
5. Provide necessary information on the protocol, medications and responsibilities of individual personnel to the sub-investigator and study collaborator, and provide guidance and supervision.
6. Screen subjects who meet the requirements of the protocol, provide the explanation of the study in writing and obtain the written consent.
7. Assume responsibility for all the medical judgment related to the study.
8. Ensure in collaboration with the director of the site that sufficient information on all clinically significant adverse events related to the study are provided to subjects throughout and beyond the period when subjects participate in the study.
9. If a subject consults other medical institution or other department, notify the physician of the medical institution or department of the subject's participation in the study, as well as the end and termination of the study in writing, and document such records.
10. In case of urgent report of a SAE, immediately notify the director of the site and the sponsor in writing.
11. Determine the need of emergency key code blinding of a subject in case of emergency.
12. Prepare correct and complete (e)CRFs, and submit them to the sponsor with electronic signature.
13. Check and confirm the contents of (e)CRFs prepared by the sub-investigator or transcribed from the source data by the study collaborator, and submit them to the sponsor with electronic signature.
14. Discuss any proposal from the sponsor including update of the protocol.
15. Notify the director of the site of the end of the study in writing.

CONFIDENTIAL

Appendix C Detailed Description of Amendments to Text

Amendments made from the first edition of this study protocol are listed below.

Page 14, 4.1 Background, Safety Summary

Existing Text

[REDACTED]

Revised Text

[REDACTED]

Rationale for Amendment

To appropriately document the summary of safety results based on the information on the incidence of adverse events in the 2 mg of TVP-1012 monotherapy group

Page 24, 7.3 Excluded Medications and Treatments

Existing Text

(15) CYP1A2 inhibitor

Revised Text

(15) CYP1A2 inhibitor (including ciprofloxacin, enoxacin, fluvoxamine, zafirlukast)

Rationale for Amendment

To specify CYP1A2 inhibitors

CONFIDENTIAL

Page 25, 7.3 Excluded Medications and Treatments

Existing Text

(17) Antidepressant (*excluding trazodone*)

Revised Text

(17) Antidepressant

Rationale for Amendment

Prohibiting concomitant use of all anti-depressants, including trazodone, was determined to be appropriate, considering the safety of subjects and potential effect on efficacy evaluations.

Page 27, 7.4 Diet, Fluid, Activity Control

Existing Text

(No description)

Revised Text

11. Subjects should avoid driving vehicles, operating machinery, and working in high areas, etc., in consideration of possible treatment-emergent dizziness, or reduced attention, concentration, or reflex function.

Rationale for Amendment

Having judged that caution should be made in light of safety of subjects based on descriptions of overseas labeling information of TVP-1012 and Japanese package insert for Parkinson's disease drugs.

## **Considerations**

This is a multicenter, open-label, long-term, extension, phase 3 study that evaluates the safety and efficacy of long-term administration of TVP-1012 at 1 mg for another 26 weeks in patients with early Parkinson's disease who have completed the 26-week treatment period in the preceding TVP-1012/CCT-001 study.

The analyses for this study will be performed using pooled data from the preceding study and this study based on data obtained after administration of TVP-1012, unless otherwise specified.

## Glossary

- Descriptive statistics:

Number of subjects, mean, standard deviation, maximum, minimum, and quartiles

- MAV:

Markedly Abnormal Value

- Treatment groups in the preceding study:

TVP-1012 1 mg and placebo groups in the preceding study. However, they are shown as “1 mg ->1 mg group” and “P ->1 mg group” respectively in this statistical analysis plan.

- Study drugs for treatment period in both studies:

Study drug for treatment period in the previous study and study drug in this study

- Number of days after administration (days):

- A) For the analyses based on the data after administration of TVP-1012

The day before the day of first TVP-1012 administration is shown as Day -1 and the day of first TVP-1012 administration as Day 1. That is, shown as follows:

[If the treatment group in the preceding study is 1 mg ->1 mg group]

Day before the day of first study drug administration for the treatment period in the preceding study:	Day -1
Day of first study drug administration for the treatment period in the preceding study:	Day 1

[If the treatment group in the preceding study is P ->1 mg group]

Day before the day of first study drug administration in this study:	Day -1
Day of first study drug administration in this study:	Day 1

- B) For the analyses based on the data after study drug administration for the treatment period in the preceding study

The day before the day of the first study drug administration for the treatment period in the preceding study is shown as Day -1 and the day of the first study drug administration for the treatment period in the preceding study as Day 1.

- Number of days after the end of administration (days):

Day 1 is defined as the day following the later of “day of the last study drug administration for the treatment period in the preceding study” or the “day of the last study drug administration in this study.”

- Protocol Deviations:

Protocol deviations in this study, unless otherwise specified.

### Definition of Visit Window

#### A) For the analyses based on the data after administration of TVP-1012

For each test, observation, and evaluation items, evaluable data (i.e., non-missing and acceptable according to the Handling Rules for Analysis Data) will be handled according to the following rules. However, the number of days after administration and number of days after the end of administration will be the contents of “For the analyses based on the data after administration of TVP-1012” in the Glossary.

Among the evaluation points, at points other than at the end of administration, evaluable data within the visit window will be used. If more than one evaluable data lies within the same visit window, the examinations, observation, and assessments with the Study Time closest to the scheduled Study Time will be used. If there are two observations equidistant to the scheduled Study Time, the later observation will be used. The size of difference from the Study Time will be determined based on the number of days after administration.

Among the evaluation points, at the end of administration, the data with the largest number of days after administration will be used among the evaluable data within the visit window.

MDS-UPDRS Part I, II, III, and IV Total Scores, MDS-UPDRS Part II + Part III Total Score, MDS-UPDRS Tremor, Muscle Rigidity, and Akinesia/Bradykinesia Scores, and MDS-UPDRS Individual Scores

Visit	Scheduled Study Time	Visit Windows	
		Number of days after administration	Number of days after the end of administration
Baseline (prior to TVP-1012 administration)	Number of days after administration: -1	-22 ~ -1	
Week 6	Number of days after administration: 42	1 ~ 55	< 8
Week 10	Number of days after administration: 70	56 ~ 83	< 8
Week 14	Number of days after administration: 98	84 ~ 118	< 8
Week 20	Number of days after administration: 140	119 ~ 160	< 8
Week 26	Number of days after administration: 182	161 ~ 202	< 8
Week 32	Number of days after administration: 224	203 ~ 237	< 8
Week 36	Number of days after administration: 252	238 ~ 265	< 8
Week 40	Number of days after administration: 280	266 ~ 300	< 8
Week 46	Number of days after administration: 322	301 ~ 342	< 8
Week 52	Number of days after administration: 364	343 ~ 385	< 8
At end of administration		1 ~ 385	< 8

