9.1.9 Procedures for Clinical Laboratory Samples

Table 9.a lists the samples to be collected for each laboratory test. All samples will be collected after fasted for more than 8 hours, whenever possible, in accordance with acceptable laboratory procedures. The maximum volume of blood at any single visit is approximately 6 mL.

Table 9.a Clinical Laboratory Tests

Hematology	Serum Chemistry	Urinalysis
Red blood cells	AST	Protein (qualitative)
Hemoglobin	ALT	Glucose (qualitative)
Hematocrit	γ -GTP	Blood (qualitative)
White blood cells with differential (neutrophil, eosinophil, monocyte, lymphocyte, and basophil)	ALP	Ketone body (qualitative)
Platelets	LDH	
	Albumin	
	Total protein	
	Total bilirubin	
	Total cholesterol	
	Triglycerides	
	Creatinine	
	Blood urea nitrogen (BUN)	
	Urine acid	
	Creatine kinase	
	Sodium	
	Potassium	
	Chlorine	
	Calcium	
	Phosphorus	
Pregnancy Test (for female subjects of childbearing potential only)		
Urine hCG (qualitative)		

The central laboratory will perform laboratory tests for hematology, serum chemistries, and urinalysis. However, the urine hCG (qualitative) will be performed at each study site for women with childbearing potential.

If subjects experience ALT or AST $> 3 \times$ ULN, follow-up laboratory tests (at a minimum, serum ALP, ALT, AST, total bilirubin, γ -GTP, and INR) should be performed within a maximum of 7 days and preferably within 48-72 hours after the abnormality was noted. (see Section 7.5 and 10.2.3)

If the ALT or AST remains elevated $> 3 \times$ ULN on these 2 consecutive occasions, the investigator or sub-investigator must contact the sponsor for consideration of additional testing, close monitoring, possible discontinuation of study medication, discussion of the relevant subject details and possible alternative etiologies.

The laboratory test results will be evaluated and maintained by the investigator or sub-investigator. And also, the investigator will maintain a copy of the reference ranges for the laboratory used.

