## Clinical Laboratory Tests

Visit	Scheduled Study Time	Visit Windows	
		Number of days after administration	Number of days after the end of administration
Baseline (prior to TVP-1012 administration)	Number of days after administration: -1	-22 ~ -1	
Week 3	Number of days after administration: 21	1 ~ 31	< 8
Week 6	Number of days after administration: 42	32 ~ 69	< 8
Week 14	Number of days after administration: 98	70 ~ 118	< 8
Week 20	Number of days after administration: 140	119 ~ 160	< 8
Week 26	Number of days after administration: 182	161 ~ 192	< 8
Week 29	Number of days after administration: 203	193 ~ 213	< 8
Week 32	Number of days after administration: 224	214 ~ 251	< 8
Week 40	Number of days after administration: 280	252 ~ 300	< 8
Week 46	Number of days after administration: 322	301 ~ 342	< 8
Week 52	Number of days after administration: 364	343 ~ 385	< 8

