## 3.2 Laboratory and Other Safety Data

### 3.2.1 Laboratory Test Results

#### 3.2.1.1 Hematology and Serum Chemistry

Analysis Set: Safety Analysis Set

Analysis Variable(s): Hematology

RBC	Hemoglobin	Hematocrit
WBC		
WBC Differentials (Neutrophil, Eosinophil, Monocyte, Lymphocyte, and Basophil)		
Platelets		
Serum Chemistry		
AST	ALT	γ-GTP
ALP	LDH	Albumin
Total Protein	Total Bilirubin	Total Cholesterol
Triglycerides	Creatinine	
Blood Urea Nitrogen (BUN)		Urine Acid
Creatine Kinase		Sodium
Potassium	Chlorine	Calcium
Phosphorus		

Categories: Results of determination based on reference values  
 [Below lower limit of reference value, Within the range of reference value, Over upper limit of reference value]

Visit:	Baseline (prior to TVP-1012 administration), Week 3, Week 6, Week 14, Week 20, Week 26, Week 29, Week 32, Week 40, Week 46, Week 52
Analysis Method(s):	The following summaries will be provided for each treatment group in the preceding study.
	
 
(1) Descriptive statistics for observed values for each visit and changes (each visit after administration [Week 3 to Week 52] - baseline [prior to TVP-1012 administration]) will be provided.
 
(2) Case Plots
 
(3) A shift table for baseline (prior to TVP-1012 administration) and each visit after administration will be provided for the results of determination based on the reference values.
 

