## 3.2.2 Vital Signs, Physical Findings, and Other Observations Related to Safety

### 3.2.2.1 Vital Signs

Analysis Set:	Safety Analysis Set
Analysis Variable(s):	
 
Body temperature
 
Systolic blood pressure
 
Diastolic blood pressure
 
Pulse rate
 

Visit:	Baseline (prior to TVP-1012 administration), Week 3, Week 6, Week 10, Week 14, Week 20, Week 26, Week 29, Week 32, Week 36, Week 40, Week 46, Week 52
Analysis Method(s):	
The following summaries will be provided for each treatment group in the preceding study.
 
If a vital sign parameter has both lower and upper MAV criteria, analysis will be performed for each. Definitions of parameters subject to this analysis and MAV criteria are given in Appendix 2 of this Statistical Analysis Plan.
 
 
(1) Descriptive statistics for observed values for each visit and changes (each visit after administration [Week 3 to Week 52] - baseline [prior to TVP-1012 administration]) will be provided.
 
(2) Case Plots
 
(3) Overall frequency distributions of MAV after the administration of TVP-1012 will be provided.
 

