**[Appendix 2]      Definition of MAV Criteria****(1) MAV Criteria****1) Vital Signs**

For each test item, those obtained until 7 days after the administration of TVP-1012 (including 7 days after the end of TVP-1012 administration and evaluable data [i.e., non-missing and acceptable according to the Handling Rules for Analysis Data]) will be subject and the determination on MAV will be conducted according to the following table. The LLN and ULN in the following table will be the lower limit and upper limit of reference values within the normal range of each test item.

Vital Signs

Test item	Gender	Age	MAV Criteria	
			Lower	Upper
Body Temperature (°C)	-	-	<35.6	>37.7
Systolic Blood Pressure (mmHg)	-	-	<90	>180
Diastolic Blood Pressure (mmHg)	-	-	<50	>100
Pulse Rate (bpm)	-	-	<45	>120

Overall determination after administration of TVP-1012

The presence or absence of MAV for each subject will be determined for each test item according to the rules (1) to (3). If a test item has both lower and upper MAV criteria, analysis will be performed for each.

- [1] If it is determined that at least 1 item among the evaluable data after the administration of TVP-1012 “meets the MAV Criteria,” it will be determined as “Yes.”
- [2] If it does not correspond to [1] and it is determined that at least 1 item among the evaluable data after the administration of TVP-1012 “does not meet the MAV Criteria,” it will be determined as “No.”
- [3] If it corresponds to neither [1] nor [2], it will be excluded from the analysis for the results of the determination.

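### The one-value-per-window rule can drop an abnormal laboratory value, and no planned laboratory table counts subjects by their worst ALT or AST

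*SAP*

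**What the plan says.** **Selection rule.** SAP, Definition of Visit Window, part A, applies to every test item: "evaluable data (i.e., non-missing and acceptable according to the Handling Rules for Analysis Data) will be handled according to the following rules". With more than one value in a window, "the examinations, observation, and assessments with the Study Time closest to the scheduled Study Time will be used". On ties, "If there are two observations equidistant to the scheduled Study Time, the later observation will be used". Repeat and unscheduled samples have no stated exemption.

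**Retest.** Protocol 9.1.9 requires follow-up tests after any ALT or AST above 3xULN. These "should be performed within a maximum of 7 days and preferably within 48-72 hours after the abnormality was noted".

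**Early termination.** Protocol 9.3.3 schedules laboratory tests and ECG within 7 days of the last dose, whenever possible.

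**Laboratory output.** SAP 3.2.1.1 plans by-visit descriptive statistics, case plots and a shift table: "A shift table for baseline (prior to TVP-1012 administration) and each visit after administration will be provided". Its three categories are below, within and above the reference range.

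**ECG output.** SAP 3.2.2.2 plans by-visit statistics, case plots and a by-visit shift in interpretation.

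**Vital signs.** SAP 3.2.2.1 adds a table over all post-dose data: "Overall frequency distributions of MAV after the administration of TVP-1012 will be provided". The rule in Appendix 2 begins "If it is determined that at least 1 item among the evaluable data after the administration of TVP-1012" and classes the subject as a Yes if that one item meets the criterion. Its criteria cover temperature, systolic and diastolic pressure, and pulse only.

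**End-of-administration row.** The MDS-UPDRS and PDQ-39 windows have a row that keeps the last value. The laboratory and ECG windows have none.

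**The concern.** Long-term safety is the primary objective, and laboratory tests and ECG are secondary safety endpoints. A reader of the report will want to know how many subjects had a marked liver enzyme elevation on TVP-1012. The planned tables cannot answer, for two reasons.

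1. Selection is by timing, so the abnormal value may not be the one tabulated.
2. Even when it is, a value above 8xULN falls in the same category as one just above ULN. Protocol 7.5 gives 3x, 5x and 8xULN a role in stopping study drug, yet no table counts subjects above them.

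The SAP solves the same problem for vital signs and gives no reason for treating laboratory tests differently.

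**Working it through.** **Inputs**
- Laboratory nominal days (SAP, Clinical Laboratory Tests): 21, 42, 98, 140, 182, 203, 224, 280, 322, 364.
- Permitted visit timing (Protocol Appendix A): nominal day ±7, for example Days 357 to 371 for Week 52. The preceding study's visit windows are not supplied; ±7 is assumed there too.
- Retest delay: preferably 2-3 days, at most 7.

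**Reproducing the windows.** Cut at the midpoint between adjacent nominal days, with a whole-day midpoint going to the later window, and close the last at 364 + 21 = 385. This gives 1-31, 32-69, 70-118, 119-160, 161-192, 193-213, 214-251, 252-300, 301-342, 343-385. All ten match the SAP.

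**Route 1: the mandated retest.** Let e be the first sample's day minus the nominal day, and k the delay to the retest. Within one window, the retest is kept if |e + k| ≤ |e|, that is, if e ≤ -k/2. The first sample must precede the nominal day by at least half the delay.

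Example: ALT above 3xULN on Day 360, retest on Day 363. Distances from Day 364 are 4 and 1, so only Day 363 enters Week 52.

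Visit days out of 15 (e = -7 to +7) on which the retest wins:

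| Delay k (days) | 2 | 3 | 4 | 5 | 6 | 7 |
|---|---|---|---|---|---|---|
| Retest kept | 7 | 6 | 6 | 5 | 5 | 4 |

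- Delays of 2-7 days: 33/90 = 37%. Over all ten laboratory visits, requiring both samples in one window: 330/900 = 37%.
- Delays of 2-3 days: 13/30 = 43%.
- First sample before the nominal day, delays 2-7: 330/420 = 79%. On or after it: 0%.

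**Sensitivity to the assumptions**
- Visits clustered around nominal (SD 3 days, truncated at ±7), delays 2-7: about 26%.
- Delay stretched to 2-10 days by laboratory turnaround, uniform visits: k = 8, 9 and 10 add 4, 3 and 3, giving 43/135 = 32%.
- Turnaround of 1-3 days added to a 2-7 day delay: 30% with uniform visits, about 17% with SD 3.
- Placebo-switch group: Day 1 is the day after VISIT 8, so the distance from nominal is the difference between two ±7 deviations, a - b. Pairs with a - b ≤ -m number (15 - m)(16 - m)/2, that is 105, 91, 78 and 66 for m = 1 to 4. Over k = 2 to 7: 105 + 2(91) + 2(78) + 66 = 509 of 225 × 6 = 1,350, or 38%. At Week 6, 10 pairs fall before Day 32 and leave the window: 509 - 60 = 449, or 33%. The conclusion is unchanged.

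**Route 2: early termination.** No retest is needed. Take a normal Week 40 sample on Day 280 and an early-termination sample on Day 298. Both lie in 252-300, at distances 0 and 18, so Day 280 is kept and the value at discontinuation is dropped. The same days share the ECG window 231-321.

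**Against a worst-value table.** A selected value cannot exceed the subject's maximum over all evaluable post-dose values. Under the Appendix 2 approach the loss is 0% by construction.

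**The case against.** **The bias is not always toward looking safer.** A reader might infer that it is. The documents do not support this: the rule selects on timing, so if enzymes are rising, the retest is higher and the by-visit table looks worse. Understatement is certain in direction only relative to a worst-value count.

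**37% is not an undercount of abnormal subjects.** It is conditional on an ALT/AST above 3xULN, and the documents give no incidence for that. A retest still above ULN leaves the shift cell unchanged, and protocol 9.1.9 itself provides for values that stay above 3xULN on two occasions. The delay also runs from when the abnormality was noted, and routine samples go to a central laboratory. All of this stands.

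**The Handling Rules may settle repeats.** They are not supplied. The follow-up panel includes INR, which is absent from Table 9.a, so entry of retests into the central laboratory data is not established. Excluding retests would close Route 1, but not Route 2 or the missing ULN-multiple counts.

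**Other outputs give cover.** They do in part. A laboratory change is an AE if judged clinically significant, including when judged beyond normal physiologic fluctuation. The patterns in protocol 7.5 call for stopping drug, and TEAEs leading to discontinuation are tabulated. ALT/AST above 3xULN with bilirubin above 2xULN and no other cause is an SAE. What remains is mainly isolated elevations that the investigator judges not significant. Case plots may show these, but the SAP does not say whether they use all values, and they give no counts. By-visit maxima come from the selected values and do not count subjects.

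**ECG.** A reader might extend the retest argument to ECG, but no ECG retest is mandated. By-visit maxima and the interpretation shift already show outliers among the selected tracings. Only early-termination or unscheduled tracings are at risk.

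**The SAP delivers what protocol 13.1.4 promises.** True. This is an improvement to the plan, not a breach of it.

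**Conclusion.** The concern holds for laboratory data. As written, the rule can drop an abnormal value from the by-visit tables by either route, and no planned laboratory table counts subjects by worst value or ULN multiple. The number of subjects with marked elevations can therefore be understated, never overstated, relative to a worst-value table.

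The 37% (33/90) is illustrative. It assumes uniform visits within ±7 days, a retest 2-7 days after sampling, and retests that are evaluable under the Handling Rules. The alternatives tried run from about 17% to 43%. The effect on the final tables cannot be sized without the incidence of elevations above 3xULN. Route 2 and the absence of ULN-multiple counts do not depend on the retest assumptions. For ECG the case is weaker and supports only an optional addition.

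**What to change.** In SAP 3.2.1.1, add two tables based on all evaluable post-dose values, including unscheduled and early-termination samples, up to <8 days after the last dose:

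1. Number and percentage of subjects, by treatment group in the preceding study, whose maximum ALT or AST exceeds 3x, 5x and 8xULN, and with ALT or AST above 3xULN together with total bilirubin above 2xULN. The cut-offs are the protocol's own and serve here only for tabulation.
2. A shift from baseline to worst post-dose category for each hematology and serum chemistry test.

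Keep the by-visit tables as they are. State in the SAP or the Handling Rules whether retests enter the analysis data, and whether case plots show all values. Optionally, add to SAP 3.2.2.2 one summary of worst ECG interpretation and maximum QTcF.

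The cost is SAP wording and a few tables from data already collected. Abnormality percentages may look slightly less favourable. No clinical rule changes.
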